6.6.2. Definitions

First Dose Date: First Dose Date of Investigational Drug: If the first diary date on the day after randomization indicates that investigational drug was taken on this day, then the first dose date will be the date after randomization (Study Day 1). In all other situations where it is known that the subject took at least one dose of medication, the first dose date will be assumed to be 1 day after the date of randomization.

Study Day: Study day will be calculated relative to the First Dose Date in the Titration Period. For any date on or after the date of first dose, study day will be calculated as assessment date - first dose date + 1. For any date prior to the date of first dose, study day will be calculated as assessment date - first dose date. There will be no Study Day 0.

Baseline Value: For non-seizure frequency assessments, the Part 1 baseline value will be the last non-missing assessment collected on or prior to the first date of dosing in Part 1. Unscheduled assessments prior to First Dose Date will be considered for selection of the baseline value. Baseline values for seizure frequency endpoints will be

Event Start and End Dates

Inssing start and end date will be imputed conservatively, i.e. missing values will be imputed in such a way that the duration of the AE is considered with the longest possible duration and such that, whenever the AE may potentially start after first date of study medication, the AE will be handled as a treatment-emergent adverse event (TEAE).

The missing Start date and End date of an AE will be imputed for the calculating treatment emergent status and assigning events of lefinitions given in the following table.

Adverse event | Partial | Missing | Mi

	Adverse event
Partial /Missing Start date	Missing day - If Adverse event day is missing but month and year is present then Impute the 1st of the month unless month is same as month of first dose of study drug in Part 1 then impute first dose date in Part 1. Missing day and month - If adverse event day and month are both missing but year is present then impute 1st January unless year is the same as first dose date in Part 1 then impute first dose date in Part 1. Completely missing - impute first dose date in Part 1 unless the end date suggests it could have started prior to this in which case impute

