	the 1st January of the same year as the end date. When imputing a start date, ensure that the new imputed date is sensible i.e., is prior to the end date of the AE.
Partial /Missing End date	Missing day - If AE end day is missing but month and year are present then Impute the last day of the month unless month is same as month of last dose of study drug then impute last dose date.
STILL SIGNI	Missing day and month - If AE has missing day and month but year is present then impute 31st December unless year is the same as first dose date then impute last dose date.
	Completely Missing - need to look at whether the AE is still ongoing before imputing a date and also when it started in relation to study drug. If the ongoing flag is missing then assume that AE is still present

(i.e. do not impute a date). If the AE has stopped and start date is
prior to first dose date then impute the 1st dose date. If the AE started
on or after the first dose date then impute the last dose date.

Data Handling for Seizure Diaries

Seizures are recorded in the Daily Seizure Diary (DSD). On each day, subjects are asked a question of whether there is a seizure to report that day. Subjects may either answer "Yes" and continue to complete more details about the seizure, or answer "No, this day has been seizure free". There will be no explicit imputation of intermittent missing data for seizure diaries. Missing seizure diary data will be handled as follows:

- If no seizures are entered in the DSD and the response to the question, is there a seizure to report that day, is "No, this day has been seizure free" then that day will have the seizure count set to 0.
- If seizures are entered in the DSD and the response to the question, is there a seizure to report that day, is "No this day has been seizure free" the seizures entered in the DSD will supersede the seizure freedom affirmation.
- If no seizures are entered in the DSD and there is no response to the question, is there a seizure to report that day, that day will be considered to have missing diary data.
- If no seizures are entered in the DSD and it is indicated that there were seizures that day, that day will be considered to have missing diary data.

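### Section 6.6.2's end-date rules for adverse events contradict its longest-duration principle and can give an end outside the recorded year or before onset

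*SAP*

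**What the plan says.** The introduction to the imputation table in Section 6.6.2 (Event Start and End Dates) sets two aims. On duration, imputation is to be such that "the duration of the AE is considered with the longest possible duration". On status, "whenever the AE may potentially start after first date of study medication, the AE will be handled as a treatment-emergent adverse event".

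The end-date rows then say:
- Day missing: last day of the month, "unless month is same as month of last dose of study drug then impute last dose date".
- Day and month missing: "impute 31st December unless year is the same as first dose date then impute last dose date".
- Wholly missing, AE stopped: the first dose date if the AE began before first dose, otherwise the last dose date.

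For a wholly missing start date the default is the first dose date, "unless the end date suggests it could have started prior to this in which case impute"; the value used under that exception is 1 January of the year in which the AE ended.

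The only plausibility check applies when a start date is imputed: "ensure that the new imputed date is sensible i.e., is prior to the end date of the AE". The end-date rows have no counterpart.

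**The concern.** The table should carry out the principle stated above it, and its end-date rows do not. One row uses first dose in its condition and last dose in its result. Three rows stop the event at last dose, although Section 9.3 keeps AE observation open to Visit 13 or 15. The derived dates can then disagree with what the site recorded, or run backwards.

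AE duration is a planned output. Section 9.3.2 calls for a median duration for AEs in at least 5% of subjects, and the addendum adds tables of mean onset and mean duration for events at that frequency. The addendum's list of changes leaves these imputation rules as they are, and Section 14 applies in general the same analyses to Cohort B.

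**Working it through.** The plan states no figure on this point, so there is none to reproduce. The rules were applied as written to example records, taking last dose to mean the last Part 1 dose.

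**Inputs.** Titration plus Maintenance is 14 weeks = 98 days (Section 4). The taper runs to day 8 after completion (Table 2), so 98 + 8 = 106 days. The double-blind period with taper or transition is 16 weeks = 112 days (Section 6.7). Visit 12 is Study Day 99 and Visit 13 is Study Day 113 (Table 5).

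**1. Year-only end, dosing crosses a year end.** First dose 15 Nov 2018, last dose 28 Feb 2019, end recorded as 2018. The recorded year equals the first-dose year, so the rule inserts 28 Feb 2019. The latest date the record allows is 31 Dec 2018. The imputed end is 31 + 28 = 59 days beyond it, in the wrong year.

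**2. Year-only end, dosing within one year.** First dose 1 Mar 2018; Visit 12 on Day 99 = 7 Jun; last taper dose 7 + 8 = 15 Jun; Visit 13 on Day 113 = 21 Jun. An end recorded as 2018 becomes 15 Jun. The latest date in the recorded year is 31 Dec, which is 15 + 31 + 31 + 30 + 31 + 30 + 31 = 199 days later. Measured against Visit 13, the shortfall is 21 − 15 = 6 days.

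**3. Day missing, month of last dose.** Same subject, end recorded as June 2018: the rule gives 15 Jun, against 30 Jun as the latest date in the month. At the extreme (last dose on the 1st of a 31-day month) the cut is 30 days.

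**4. Onset after the last taper dose.** Same subject, AE onset 18 Jun, which is within AE observation because Visit 13 is 21 Jun.

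| End date recorded | Rule that applies | Imputed end |
|---|---|---|
| June 2018 | month equals month of last dose | 15 Jun |
| 2018 | year equals year of first dose | 15 Jun |
| missing, AE stopped | began on or after first dose | 15 Jun |

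Each imputed end is three days before onset, and no check catches it.

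**5. How often dosing crosses a year end.** If first doses are spread evenly over 365 days, the share of subjects is (d − 1)/365 for d dosing days: 97/365 = 26.6% (d = 98), 105/365 = 28.8% (d = 106), 111/365 = 30.4% (d = 112). Even enrolment is an assumption.

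**6. Wholly missing start.** First dose 1 Mar 2018, AE end 30 Apr 2018. If the exception is triggered whenever earlier onset is possible, the start becomes 1 Jan 2018 and the AE is pre-treatment, although onset from 1 Mar to 30 Apr is equally open. If it is triggered only when the end precedes first dose, the start is 1 Mar and the AE is treatment-emergent.

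**The case against.** A reader might infer that these rules corrupt treatment-emergent status and period assignment in general. They do not. Section 9.3 sets both from the start date, so the end-date rules cannot change them. The two rows for partly missing start dates protect treatment-emergent status.

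The wholly missing start is the one place where status is at risk, and there the fault depends on reading. The default is first dose. On the literal reading the exception would take in almost every end date and leave the default little to do. The introductory sentence favours the narrower meaning. This is fair. Even so, the row does not state the narrower condition, and two programmers could derive different flags from it.

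Three further inferences go too far:
- The 27–30% in step 5 is not an error rate. It is an assumed share of subjects, and the year-only rule also needs an AE whose end day and month are both missing.
- An AE recorded as ending in 2019, in a subject whose dosing began in 2018, is given 31 December 2019. That follows the longest-duration principle and is no fault.
- Ending a stopped AE of pre-dose onset at first dose also departs from the principle. But such an AE is not treatment-emergent, and the planned duration tables cover treatment-emergent events only.

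The window for an end before onset is narrow: 6 days at nominal visit days for a tapered subject, and it largely vanishes for those continuing into Part 2, who are dosed through the transition. No p-values are planned for AEs, and efficacy is untouched. These points limit the effect. They do not remove the mismatch in the year-only rule or the missing check on imputed ends.

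**Conclusion.** The end-date rules are wrong as written, and showing so needs no interpretation. The year-only rule can contradict the recorded year. The cut at last dose contradicts the stated principle. An imputed end can precede onset with nothing to stop it.

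The effect is descriptive and confined to the AE duration summaries. Durations can be too long (59 days in example 1) or too short (6 days against Visit 13, or 199 days against the recorded year, in example 2). The number of partly dated AEs is not given, so the effect on the reported medians and means cannot be sized.

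The wholly-missing-start exception is a separate, lesser point: ambiguous wording which, taken literally, works against the status aim in the same section. Wholly missing start dates are probably rare.

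**What to change.** Replace the end-date rows with one principle: impute the latest date consistent with the recorded year and month, capped at the subject's last Part 1 AE observation date where that date is compatible with the recorded parts. For a stopped AE with no end date, use the last Part 1 AE observation date. Require every imputed end to be on or after the start.

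For a wholly missing start, impute the first dose date unless the end date is before first dose.

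The cost is a few lines in the SAP table and a small change to the AE derivation program, plus a rerun of the duration summaries for any affected records. No new data are needed.

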8.4.3. Seizure-Free Days

Seizure free days will be taken from the parent/caregiver diary data.

A seizure free day with no seizures leading to drops will be defined as a day for which diary data are available and with no ESC-defined drop seizures. A day without countable motor seizures will be defined as a day for which diary data are available and with no countable motor seizures. The total number of countable seizure-free days and drop seizure-free days will be summed for the entire T+M period and similarly for the baseline period.

Seizure-free days per 28 days at baseline = (number of seizure free days during baseline)*28/ (number of days during baseline with non-missing diary data)

Seizure-free days per 28 days during T+M Period = (number of seizure free days during T+M Period)*28/ (number of days during T+M Period with non-missing diary data)

Statistical comparison of treatment groups and placebo on the number of seizure free days per 28 days and drop seizure-free days per 28 days during T+M using the baseline as covariate will be done with a similar non-parametric ANCOVA model as described for the primary analysis.

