8.4.4. Duration of the Longest Interval between Seizures Resulting in Drops

The duration of longest interval between seizures resulting in drops (in days) will be analyzed using nonparametric methods.

For each subject, the duration of the longest interval between seizures resulting in drops (i.e., ESC confirmed) will be calculated over the entire T+M period. This will be derived as the maximum of the number of consecutive days between seizures resulting in drops. The length of the intervals between seizures resulting in drops will be calculated as below, after which the duration of the longest interval between convulsive seizures will be derived.

If a subject has a missing diary day within an otherwise seizure-free interval, that day is counted towards the duration of the seizure free interval. However, if a subject has two consecutive days of missing diary data, the current seizure-free interval will end on the first date of missing diary data, and a new one begun on the next date that diary data are available and no seizure occurs. [In that case, for purpose of calculation of this variable, all intervening days, after the 2nd day, with missing diary data, will be assumed to have a seizure with drops occurrence, until the first available date with non-missing diary data.]

Let Date0 (=Day1) be the first day of treatment. If a seizure resulting in a drop occurs on five days having dates as Date1, Date2, Date3, Date4, and Date5, where Date5>Date4>Date3>Date2>Date1≥Date0, and let LDT = Last date of treatment in the maintenance period, where LDT ≥ Date5, then the time interval between convulsive seizures will be calculated as follows:

Version 2.0

Syneos Health #1009529A

I1=Date2 - Date1

12=Date3 - Date2

13=Date4 - Date3,

14=Date5 - Date4.

For completeness, we calculate the time to the first seizure as

10=Date1 - Date0,

and the time from the last seizure to end of treatment as

15 = LDT - Date5.

Here the duration of the longest interval =Maximum (10, 11, 12, 13, 14, 15).

If the subject does not experience a seizure during treatment, then the last available diary date will be used to compute the duration of the longest interval as follows:

The longest interval=last available diary date DateO

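### A single day with seizures affirmed but no details entered is bridged as drop-seizure-free in the longest-interval endpoint (SAP 6.6.2 with 8.4.4)

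*SAP*

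**What the plan says.** SAP 6.6.2 (Data Handling for Seizure Diaries) distinguishes four kinds of day. Two of them become missing. One is the blank day, with no entry, on which "there is no response to the question, is there a seizure to report that day, that day will be considered to have missing diary data". The other is the day with no entry on which "it is indicated that there were seizures that day, that day will be considered to have missing diary data". The section also states: "There will be no explicit imputation of intermittent missing data for seizure diaries". In a further case, where seizures are entered but the daily question was answered as seizure-free, the entered seizures prevail.

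SAP 8.4.4 defines the longest interval between ESC-confirmed drop seizures over T+M and handles missing days by run length. For one day: "If a subject has a missing diary day within an otherwise seizure-free interval, that day is counted towards the duration of the seizure free interval". For two: "if a subject has two consecutive days of missing diary data, the current seizure-free interval will end on the first date of missing diary data". Missing days beyond the second, "with missing diary data, will be assumed to have a seizure with drops occurrence, until the first available date with non-missing diary data". None of these rules asks why the day is missing.

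The endpoint is listed as an additional secondary one in SAP 5.3 and tested by Wilcoxon rank-sum for each dose against placebo. It is not among the six steps in SAP 8.1.

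**The concern.** An affirmed day without details carries information that a blank day does not: someone reported at least one seizure. Section 6.6.2 discards that information, and 8.4.4 then gives the day the favourable treatment meant for an isolated gap. The result orders the evidence the wrong way round. One day with a seizure report extends the interval, while two days with no report at all end it. It also sits badly with the plan's own preference elsewhere in 6.6.2, where evidence of a seizure overrides a seizure-free answer.

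At stake is an endpoint built on a maximum. One bridged day between two runs joins them into one, so a single diary entry can change a subject's value substantially.

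**Working it through.** The plan states no figure on this point, so there is nothing to reproduce. The check applies the two rules together.

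**Rules side by side**

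| Diary content | Status in 6.6.2 | Effect in 8.4.4 |
|---|---|---|
| One blank day | missing | bridged |
| One day, seizures affirmed, none entered | missing | bridged |
| Two consecutive missing days, either kind | missing | interval ends on the first |
| Third and later consecutive missing days | missing | assumed drop-seizure days |

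**Worked diary (assumed data).** T+M is planned for 14 weeks (SAP 8.2.1), so 14 × 7 = 98 days. Date0 is Day 1 and the last treatment date is Day 98. Drop seizures fall on Days 11, 21, ..., 91.

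- All entries complete: I0 = 11 − 1 = 10, each inner interval = 10, and the last = 98 − 91 = 7. The maximum is 10 days.
- Day 51 affirmed but undetailed, SAP rules: Day 51 is bridged, so the interval from Day 41 to Day 61 is 61 − 41 = 20. The maximum is 20 days.
- Day 51 affirmed but undetailed and allowed to end the interval: 51 − 41 = 10 and 61 − 51 = 10. The maximum is 10 days.

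If the Day 51 seizure was a drop, 10 is right and the SAP value is twice too long. If it was not a drop, 20 is right and the alternative rule is too short.

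**Average effect (simulation, 98 days, 4000 runs per setting).** Three things are assumed: the daily drop-seizure probability, the share of seizure days left undetailed, and that every undetailed day was a true drop day. Cells show the mean longest interval with complete entries → under the SAP rules.

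| Daily probability | 2% undetailed | 5% undetailed | 10% undetailed |
|---|---|---|---|
| 0.1 | 27.41 → 27.77 | 27.47 → 28.39 | 27.42 → 29.47 |
| 0.3 | 11.56 → 11.76 | 11.59 → 12.09 | 11.66 → 12.76 |
| 0.6 | 5.55 → 5.70 | 5.59 → 5.93 | 5.56 → 6.24 |

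The mean rises by 0.15 to 0.36 day at 2%, 0.34 to 0.92 day at 5%, and 0.68 to 2.05 days at 10%. The median moves by 0 or 1 day. The upward direction follows from the third assumption and is not evidence for it.

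**The case against.** The strongest objection is that the daily question concerns any seizure. Appendix 1 lists fourteen categories, of which five are drop types, and drop status also needs ESC approval for the individual subject. An affirmed day without details therefore does not establish a drop seizure, and calling it missing for a drop endpoint is defensible. This stands as a limit on direction and size. It does not justify giving an affirmed day the same one-day bridge as a blank one, when the plan lets two uninformative days end the interval.

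One could also read the 8.4.4 condition of an otherwise seizure-free interval as already excluding affirmed days. Section 6.6.2 defines such a day as missing, however, and 8.4.4 acts on missing days, so the text needs clarifying even on that reading.

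A reader might infer more than the documents support:

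- *That seizure-free days (8.4.3) are inflated.* That section divides by the "number of days during T+M Period with non-missing diary data" and does not count an affirmed, undetailed day as free. The day leaves both numerator and denominator. With an assumed 98 days, 20 free and 10 undetailed, the SAP gives 20 × 28/88 = 6.36. If all ten held relevant seizures the value should be 20 × 28/98 = 5.71. If none did, it should be 30 × 28/98 = 8.57. The SAP value lies between, so the direction is unknown.
- *That the primary endpoint is biased towards fewer seizures.* In the worked diary, DSF falls from 28 × 9/98 = 2.57 to 28 × 8/97 = 2.31 when the lost day held a drop seizure. Removing days that held only non-drop seizures shrinks the denominator alone and raises DSF. The rule also acts on Baseline, so the direction for percent change is undetermined.
- *That undetailed entries cluster on bad days.* This is plausible, but the plan does not say so.

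**Conclusion.** The point holds for the longest-interval endpoint. As written, 6.6.2 and 8.4.4 together let an isolated positive seizure report lengthen a drop-seizure-free interval. For one subject the effect can be a doubling (20 against 10 days in the assumed diary, if the undetailed seizure was a drop). On average it is modest, about 0.2 to 2.1 days in the mean under assumed rates of 2% to 10% with every such day a drop day. The plan gives no frequency for these days. The same rule applies in all blinded arms, so a distorted treatment comparison would need such days to be common or to differ between arms.

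The reach is one additional secondary endpoint outside the testing hierarchy. The bridging rule does not enter the primary or key secondary tests. No general claim that the diary rules favour fewer seizures is supported.

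**What to change.** In SAP 8.4.4, separate two kinds of missing day: no response, and seizures affirmed with details missing. Apply the one-day bridge only to the first kind. Let a day of the second kind end the interval, as a drop-seizure day would. Report the number of affirmed, undetailed days by arm and by period (Baseline, T+M), so that a reader can see whether the rule matters and whether the arms differ. The DSF formula in 8.2.1 and the seizure-free-day formula in 8.4.3 can stay as they are.

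The cost is a few lines of text, one flag in the diary derivation and one small table. The downside is slight conservatism: where the undetailed seizure was not an ESC-confirmed drop, the interval is cut too early. That is in keeping with how 8.4.4 already treats two or more consecutive missing days.

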6.7. VISIT WINDOWS

The following rules will be used to window data into treatment periods for by treatment period tabulations. For all by-visit tabulations, the nominal visit as recorded on the electronic Case Report Form (eCRF) will be used.

The following are the definitions for associating dates with the treatment periods of Part 1.

Baseline Period	The Baseline Treatment period will be the 28 days immediately prior to the date of the Study Day 1.
Double Blind	The Double-Blind Treatment Period start date is the date of
Treatment Period	first full daily dose (i.e. Study Day 1). The Double-Blind
Sell Call	Treatment Period end date is the last date the subject was on study treatment in Part 1.
Chy, Oblig	The Double-Blind Treatment Period consists of 16 weeks from first treatment start date, which includes 2 weeks of
S. S.	Titration period, 12 weeks of Maintenance period and 2 weeks of Taper/Transition period. The end date for efficacy
	analyses is the last day of Maintenance treatment, or Visit 12; the end date for safety analyses is the last day of

version 2.0	Syneos Health #1009529	7A
	Taper/Transition, which would be considered the date at Visit 15.	ation
	For subjects who discontinue early from the study, the double-blind treatment period end date for efficacy analyses will be the date at the early termination visit (Visit 12); the end date for safety analyses would be the date of Visit 13. If a taper is not conducted, the end date for both analyses would be Visit 12.	alithorization ereof.
Titration Period	The Titration Period begins on the first full day of treatment (Study Day 1) and extends through Visit 6 (when the subject has reached their randomization dose). The Titration Period applies to all subjects including placebo recipients. If a subject withdraws from the study prior to treatment in the maintenance period, all safety assessments and events up to and including the date of study withdrawal will be tabulated in the titration period.	ere .
Maintenance Period	The Maintenance Period covers the 12 weeks following the end of the titration period. It begins on the date of Visit 6 + 1 day and extends through the end of study/early termination visit (Visit 12).	
Titration + Maintenance Period (T+M)	The T+M period combines the Titration and Maintenance periods, beginning on the date of first treatment (Study Day 1) and extending through the end of study/end of treatment visit (Visit 12).	
Taper/Transition Period	The Taper/Transition period consists of 2 weeks starting from end of study/early termination visit (Visit 12) + 1 day through Visit 13 (Taper) or Visit 15 (Transition to Part 2). For subjects who are not entering into the Part 2 of the study, subjects will gradually be tapered off of study medication. For subjects who are entering Part 2, subjects will enter the transition phase where all subjects will be on a dose of 0.2	
	mg/kg/day at the end of this phase.	

